9.7 Incidental findings

An incidental finding is one that has potential health or reproductive importance which is discovered unexpectedly in the course of conducting research but is unrelated to the purpose or aims of the trial – e.g. an abnormal laboratory safety test result. Depending on the nature of the finding, the subject might have to be withdrawn, or vaccinations discontinued, per Section 5.4, and his/her GP informed if consent to do so is received from the participant.

9.8 Early Stopping of Follow-up

If a participant chooses to discontinue injections, they should always be followed up for safety and pregnancy events providing they are willing. If they do not wish to remain on trial follow-up, however, their decision must be respected, and the participant will be withdrawn from the trial completely. The Chief Investigator should be informed of this in writing using the appropriate documentation.

Medical data collected in the trial will be kept for research and analysis purposes are pseudo-anonymised. Consent for future use of stored samples already collected can be refused when leaving the trial early (but this should be discouraged and should follow a discussion).

9.9 Loss to Follow-up

Study staff will make every effort to contact participants who do not attend their scheduled visits. At least three attempts will be made to contact the participant during the period from enrolment through to Week 52.

Participants who are lost to follow-up after at least three attempts to contact them will be able to return to follow-up if they make contact at a later date before trial closure.

Participants will be followed up in the long-term through usual mechanisms and with the appropriate consent, which may include flagging via NHS Digital, or similar approaches.

9.10 Trial Closure

The trial will be closed when all participants have made their final follow-up visit and assessments are completed including those to determine resolution of any adverse events, the data entered into the database, checked and the database locked.

10. STATISTICAL CONSIDERATIONS

10.1 Method of Randomisation

Participants will be randomised to receive LNP-MARVsaRNA, LNP-EBOVsaRNA or LNP-LASSAsaRNA vaccines either singly or in combination, with equal allocation ratio (see Figure 1). This is a single-blind trial, in which participants and laboratory staff will be blinded to the dose allocation, while clinic staff will remain unblinded.

10.2 Outcome Measures

The outcome measures are:

- Solicited local injection site reactions starting within 7 days of administration of the vaccine: pain, tenderness, erythema, swelling
- Solicited systemic reactions starting within 7 days of administration of the vaccine: pyrexia, fatigue, myalgia, headache, chills, arthralgia
- Unsolicited adverse reactions (ARs) throughout the trial period (including serious ARs)
- Serious Adverse Events
- Unsolicited adverse events throughout the trial period
- The titre of vaccine-induced serum IgG binding antibody responses to the Marburg virus, Ebola virus and Lassa virus surface glycoprotein 2 weeks after the second vaccinations

The exploratory outcome measures are:

- The titre of serum neutralising antibodies 2 weeks after the second vaccination in the Marburg, Ebola and Lassa pseudovirus-based neutralisation assay
- Cell-mediated vaccine-induced immune responses measured by T and B cell ELISpot in participants in the dose escalation and evaluation parts
- Cell-mediated vaccine-induced immune responses measured by flow cytometry and intracellular cytokine staining in participants in the dose escalation and evaluation parts
- Serum markers of innate immune response

10.3 Sample Size

10.3.1 SAFETY

It is not the remit of this Phase I trial to recruit a sufficient number of participants to be statistically confident about the differences between groups, and thus no formal hypothesis testing will be carried out for safety. By the end of this trial 8 participants will have been exposed to each vaccine alone or in combinations and this provides confidence around the response/event proportions of 0–100% in Table 7.

Table 7: confidence around the response/event proportions per dose irrespective of schedule

Number of "responders"	Proportion if n=8	95% confidence interval ¹
	11 11-8	
0	0%	0 – 32%
1	12.5%	1 – 47%
2	25%	7 – 59%
3	37.5%	14 – 69%
4	50%	22 – 78%
5	62.5%	31 – 86%
6	75%	41 – 93%
7	87.5%	53 – 99%
8	100%	68 - 100%

¹ Wilson interval (suitable for small sample sizes)

10.3.2 IMMUNOGENICITY

A total of 40 participants will be included in the randomised evaluation of immunogenicity, 8 participants per group. The primary analysis will compare binding antibody responses to Ebola virus, Lassa virus and Marburg virus glycoproteins at 14 weeks (2 weeks after the booster at 12 weeks). It is difficult to give an estimate of the power of group comparisons using quantitative antibody titre outcomes at this stage as this is dependent on the number of responders, and the large number of experimental parameters in this experimental trial. The main objective of groups 1-5 is to assess whether overall immune responses to individual Ebola, Lassa and Marburg LNP saRNA vaccines given alone are similar to those administered in combination. No formal hypothesis testing will be performed for immunogenicity endpoints; all comparisons will be descriptive. Ideally, binding and neutralisation antibody should be observed in 100% of participants. With a sample size of 8 participants per group, the lower 5% CI for the response rate is 68-100% if there are no non-responders, and 41-93% if there are two non-responders in any group. The number of 'responders' in each assay will be presented for each timepoint and group as a proportion with a 95% confidence interval. A 'responder' will be defined as a participant in whom a response was detected in two weeks after the final vaccination immunogenicity sample. A positive result will be defined relative to a pre-defined cut-off threshold value and assays will be validated using predefined thresholds based on the responses to positive and negative control stimuli. More information on the assay and definition of positive results will be supplied

in the SAP. Titres of antigen specific antibodies will be described by timepoint and group and compared using rank tests, where appropriate.

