3. LAY SUMMARY

EML-Vac is a trial that is looking at new RNA vaccines against the Marburg, Ebola and Lassa Fever viruses which are the major causes of viral blood (heamorrhagic) fever. The aim of the trial is to assess the safety of these vaccines alone and in combination, since this will be the first time that these have been used in humans. But this trial is NOT looking at whether or not the vaccines are effective in terms of protection. It is just assessing the safety of these vaccines and how well the immune system responds to the vaccine.

EML-Vac saRNA Vaccines

Since this is the first time these vaccines have been used in humans, the safety will be assessed in healthy young adults. 40 participants aged 18-50 years will be randomised to one of five different groups receiving either Ebola, Marburg or Lassa self-amplifying RNA (saRNA) vaccines individually or in combination by injection into the muscle. Participants will receive prime and boosting immunisations 12 weeks apart. They will be careful monitoring for any reactions to the vaccine.

There are likely to be mild side-effects near to the injection site. There may also be more general side-effects such as headache, temperature and chills. Participants will be asked to record any symptoms in an online diary. In order to see how well the immune system is responding, participants will need to give blood samples several times during the first 4 weeks; then for 24 weeks following their boosted immunisation and finally at 12 months to assess durability of response. This will happen at one trial centre. If any part of the trial shows that either dose is unsafe or poorly tolerated, it will be omitted from further trial.

Although there have been no clinical studies using these three saRNA vaccines, a previous first-in-human trial (COVAC-1) evaluated the safety and immunogenicity of an saRNA vaccine encoding the spike glycoprotein of SARS-CoV-2, the causative agent of COVID-19 in over 200 participants (phase I/IIa). The saRNA vaccine was administered as prime and boost intramuscular injections, 4 and 14 weeks apart at dose levels of 0.1, 0.3, 1, 2.5, 5 and 10 μ g and participants were followed up for an additional 48 weeks. Safety data have shown that this vaccine was safe and well tolerated and the majority of reactions following vaccinations were mild or moderate. The majority of solicited adverse events reported within 7 days after the prime and boost vaccination were mild.

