4.1.1 LNP-MARVSARNA-01, LNP-EBOVSARNA-01 AND LNP-LASSASARNA-01 EVALUATION

The initial dosing of the sentinel participant for each of the five groups will proceed through groups 1-3 administering either LNP-MARVsaRNA-01 (5 μ g), LNP-EBOVsaRNA-01 (4 μ g), or LNP-LASSAsaRNA-01 (4 μ g), group 4 administering LNP-MARVsaRNA-01 (5 μ g) plus LNP-EBOVsaRNA-01 (4 μ g) (9 μ g total RNA) and group 5 administering LNP-MARVsaRNA-01 (5 μ g), LNP-EBOVsaRNA-01 (4 μ g), or LNP-LASSAsaRNA-01 (4 μ g), (13 μ g total RNA). Participants and laboratory staff will be blinded to the administered dose:

- 1. The first sentinel participant will receive 5 μ g of LNP-MARVsaRNA, plus two buffered saline placebo injections and be invited to enter information on local and systemic reactions, into an online diary, that evening and daily thereafter for 6 days.
- 2. At 1 day post immunisation, the participant will attend the trial site to review AEs and donate blood to measure innate immune responses.
- 3. At 48 (-/+5) hours post-vaccination the team will call the participant and go through his/her diary. If the reactions are Grade 1-2, or transient Grade 3 that resolve within 24 hours, the second participant may receive 4 µg of LNP-EBOVsaRNA, plus two buffered saline placebo injections.
- 4. At 1 day post immunisation, the second participant will attend the trial site to review AEs and donate blood to measure innate immune responses.
- 5. At 48 (-/+5) hours post-vaccination the team will call the second participant and go through their diaries. If the reactions are Grade 1-2, or transient Grade 3 that resolve within 24 hours, the third participant may receive 4 µg of LNP-LASSAsaRNA, plus two buffered saline placebo injections.
- 6. At 1 day post immunisation, the third participant will attend the trial site to review AEs and donate blood to measure innate immune responses.
- 7. At 48 (-/+5) hours post-vaccination the team will call the third participant and go through their diaries. If the reactions are Grade 1-2, or transient Grade 3 that resolve within 24 hours, the fourth participant may receive 5 µg of LNP-MARVsaRNA plus 4 µg of LNP-EBOVsaRNA, plus one buffered saline placebo injection.
- 8. At 1 day post immunisation, the fourth participant will attend the trial site to review AEs and donate blood to measure innate immune responses.

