- 9. At 48 (-/+5) hours post-vaccination the team will call the fourth participant and go through their diaries. If the reactions are Grade 1-2, or transient Grade 3 that resolve within 24 hours, the fifth participant may receive 5 μ g of LNP-MARVsaRNA plus 4 μ g of LNP-EBOVsaRNA plus 4 μ g of LNP-LASSAsaRNA

- 10. At 1 day post immunisation, the fifth participant will attend the trial site to review AEs and donate blood to measure innate immune responses.
- 11. At 48 (–/+5) hours post-vaccination the team will call the fifth participant and go through their diaries. If the reactions are Grade 1-2, or transient Grade 3 that resolve within 24 hours, the dose evaluation cohort of remaining 35 participants may start to be enrolled and randomised into one of the 5 groups to receive their first immunisation.
- 12. Sentinel participants will be evaluated again as above after receiving their second dose. If the reactions are Grade 1-2, or transient Grade 3 that resolve within 24 hours, the cohort of remaining 35 participants may receive their second dose

The steps above describe the fastest plan to enrol into the 5 groups and is justified based on previous experience with this self-amplifying RNA platform. However, if there are persistent Grade 3 reactions observed in any of the sentinels, the team will invite the affected participant to attend the trial site in order to evaluate these and will proceed to vaccinate a second sentinel within the same group. The group will not be changed until at least 1 participant has provided acceptable safety data to at least 48 (–/+5) hours post-vaccination. If 2 or more of the participants at any dose level in this part of the trial have persistent Grade 3 (or worse) reactions, or if 1 or more has a serious adverse reaction, the dose will not be expanded, and the trial stopping rules described below (7.1.5) will be triggered.

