11.1.1 SAFETY AND RIGHTS OF PARTCIPANTS

The pre-clinical data available for LNP-MARVsaRNA, LNP-EBOVsaRNA and LNP-LASSAsaRNA for four species (mice, guinea pigs, rats and pigs) suggest that this product will be similar to licensed RNA vaccines and cause mild-moderate reactions that are transient. However, this is a first-in-human trial and therefore there will be a sentinel cohort with one individual allocated to each group. There will be immediate review of notable and serious adverse events with onward reporting to the TSC, and clear indications for pausing injections in individuals and the trial.

It will be necessary to hold personal contact details in order to collect the data on reactogenicity. The justification for this will be explained in the PIS as well as the storage and destruction of these data after the trial.

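### The protocol counts 40 participants as randomised, but the first five are placed in Groups 1 to 5 by dosing order, so only 35 are randomised

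*Protocol*

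**What the plan says.** **Places that present 40 as randomised**

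- Section 10.3.2: "A total of 40 participants will be included in the randomised evaluation of immunogenicity, 8 participants per group".
- Section 3, Lay Summary: "40 participants aged 18-50 years will be randomised to one of five different groups".
- Section 2, Summary of Trial: the Randomisation row gives 40 across the five cohorts.
- Table 2: randomisation is marked at Visit 2 in the schedule for all groups, with no exception for sentinels.
- Section 10.1 gives no head count. It describes allocation to the vaccines "either singly or in combination, with equal allocation ratio" and does not mention sentinels.

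**Places that assign the sentinels differently**

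- Section 4.1.1 opens: "The initial dosing of the sentinel participant for each of the five groups will proceed through groups 1-3", and then continues to Groups 4 and 5. Its numbered steps give the first participant the Group 1 regimen, the second Group 2, the third Group 3, the fourth Group 4 and the fifth Group 5. Each step depends on the previous sentinel's reactions at about 48 hours.
- Section 4.1.1, step 11: after the fifth sentinel is reviewed, the "remaining 35 participants may start to be enrolled and randomised into one of the 5 groups to receive their first immunisation".
- Section 11.1.1: "there will be a sentinel cohort with one individual allocated to each group".
- Section 4.1.1, closing paragraph: a second sentinel may be vaccinated in the same group after a persistent Grade 3 reaction.

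**The concern.** Step 11 of Section 4.1.1 speaks of a remainder of 35, which places the five sentinels inside the total of 40. Their group follows from their place in the dosing sequence. The two descriptions cannot both be right: either 40 are randomised, or 35 are.

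This matters because Section 10.3.2 names a between-group comparison of binding antibody at 14 weeks as the primary analysis. Its stated aim is to see whether responses to the vaccines given alone resemble those given in combination. Calling that comparison randomised is a claim about the design. For the sentinels the claim fails in two ways: no random mechanism assigns the group, and the clinic staff, who are unblinded, know the next sentinel's group before that person is enrolled. Concealing the next allocation is one of the main purposes of randomisation.

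The documents also do not say how the counts change if a second sentinel is used.

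**Working it through.** **Inputs.** Five groups of 8 (Table 1 and Section 10.3.2); one sentinel per group (Sections 4.1.1 and 11.1.1); 35 randomised after the sentinels (Section 4.1.1, step 11); equal allocation (Section 10.1); Wilson 95% intervals (footnote to Table 7), with z = 1.96.

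**1. The plan's own figures.**
- Enrolled: 5 × 8 = 40, which equals 5 sentinels + 35 remaining. The total of 40 reproduces as the number enrolled.
- With p = x/n, the Wilson limits are [p + z²/(2n) ± z·√(p(1−p)/n + z²/(4n²))] / (1 + z²/n).
- 8 of 8: 67.6-100%. The protocol says 68-100%.
- 6 of 8: 40.9-92.9%. The protocol says 41-93%.

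**2. The randomised number.**
- 40 − 5 = 35.
- 35 / 5 = 7 per group. This is inferred from equal allocation; the protocol does not state it.
- Non-randomised share: 5/40 = 1/8 = 12.5%, the same in every group.

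**3. Precision in the randomised set.**

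| Non-responders | All treated, n = 8 | Randomised only, n = 7 |
|---|---|---|
| 0 | 67.6-100% | 64.6-100% |
| 2 | 40.9-92.9% | 35.9-91.8% |

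With x = n the lower limit reduces to n/(n + z²): 8/(8 + 3.84) = 0.676 and 7/(7 + 3.84) = 0.646. The difference is 3 percentage points. With two non-responders the lower limit falls by 5 points (40.9 − 35.9).

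**4. If one group needs a second sentinel.**
- If the group total stays at 8, that group has 8 − 2 = 6 randomised, and the trial has 40 − 6 = 34.
- If 35 are still randomised at 7 per group, that group has 2 + 7 = 9, and the trial has 6 + 35 = 41.

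The protocol does not say which applies.

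**The case against.** The strongest reply has four parts.

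**Consequences are small.** Section 10.3.2 says that all comparisons are descriptive, with no formal hypothesis testing, and there is no power calculation to upset. The sentinels meet the same eligibility criteria and follow the same schedule as everyone else, and each group has one, so the groups stay numerically balanced. This stands, and it limits the weight of the point.

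**Analysis sets belong in the SAP.** Section 10.4 defers the full analysis to a separate plan, which could choose 35, 40 or both. This stands for the choice of set. It does not cover the count: the SAP cannot correct the number the protocol says is randomised, nor make a fixed-order assignment random.

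**Table 2 shows randomisation at Visit 2 for everyone.** One could suppose that sentinels also pass through the randomisation system. But Section 4.1.1 fixes their group by sequence and starts randomisation with the 35, so the Table 2 entry adds to the inconsistency.

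**The second-sentinel case is a contingency.** Section 4.1.1 presents its sequence as the fastest route, so 35 is a base case, and an extra sentinel could be absorbed by randomising fewer to that group. That is fair; the protocol only fails to say so.

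Stronger readings are tempting but are not supported:

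- *A reader might infer that the first five are effectively unblinded.* They receive three injections per visit with blinding labels on the syringes, like everyone else. Nothing shows that participants know their place in the sequence. Whether the laboratory could work out the group depends on sample coding, which the protocol does not describe; it says only that personal data leave the site under a trial ID. This is a possibility, not a finding.
- *A reader might infer a large bias from the weight of one sentinel.* One value differing 10-fold moves a geometric mean of eight by a factor of 10^(1/8) = 1.33. That is true of any single participant, randomised or not, and nothing in the documents suggests that a sentinel would differ in this way.
- *A reader might infer that the intervals in Section 10.3.2 are wrong.* They are correct for the eight treated per group.

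**Conclusion.** The contradiction stands. Section 10.3.2 and the lay summary give the randomised number as 40, and the Section 2 Randomisation row lists the same 40. By Section 4.1.1 it is 35, or 7 per group if the equal ratio is applied to those 35. It is lower still if a second sentinel is used and the group total stays at 8. One in eight observations per group in the primary immunogenicity comparison has neither random assignment nor concealed allocation.

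The fault is a misdescribed design property, not lost power. In the base case the lower Wilson limit with no non-responders moves from 68% to 65%. The safety analysis of all treated participants is unaffected. The conclusion rests on reading the fixed dosing order as the means of assigning sentinels, which is the only means the protocol describes. The point should be corrected, but it does not undermine the trial.

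**What to change.** **Preferred change.**
- In the Section 2 Randomisation row, the lay summary and Section 10.3.2, state that 5 sentinels are assigned by dosing order and 35 participants are randomised.
- In Section 10.1 and Table 2, except the sentinels from randomisation.
- State how the counts change if a second sentinel is used.
- Present the between-group immunogenicity comparison for the randomised 35 beside all 40, and keep all 40 for safety.

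The cost is a few sentences and one additional set of rows in the immunogenicity tables. The stated randomised number falls from 40 to 35.

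**Alternative.** Screen five sentinel volunteers before the first is dosed, and assign them to the five slots by a random permutation from the randomisation system, leaving the dosing sequence unchanged. This needs one list of length five and makes 40 randomised true in the base case. It does not cover a second sentinel, and it does not hide the group from anyone who knows the dosing order.

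**Either way.** Give laboratory samples codes unrelated to entry order. This removes the possible route to laboratory unblinding at almost no cost.

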3.1.6 Previous studies

3.1.6.1 Pre-clinical

The 3 vaccines, LNP-MARVsaRNA-01, LNP-EBOVsaRNA-01 and LNP-LASSAsaRNA-01 that will be tested in the EML-Vac clinic trial have all shown to induce robust immune responses in pre-clinical models administered at a 5 µg dose alone or together via the intramuscular route (see Investigators brochure). In addition, in the pig model, cross-reactive Ebola-specific IgG was detected in animals immunised with LNP-

saRNA Marburg vaccine. The protective effect of all 3 vaccines was shown in efficacy studies in guinea pigs, whereby 100% of animals vaccinated with either 1 μ g/dose of LNP-MARVsaRNA-01, 1 μ g/dose of LNP-EBOVsaRNA-01 or 1 μ g/dose of LNP-LASSAsaRNA-01 were protected from disease progression respectively following challenge with 1,000 TCID50 of virus 4 weeks post vaccination.

In a pivotal nonclinical toxicology study (Labcorp Study no. 8494899) conducted to Good Laboratory practice (GLP) in rats, the toxicity of 5 μ g/dose of LNP-MARVsaRNA-01 and 15 μ g/dose EML-saRNA (three VEEV-saRNAs encoding the glycoproteins of Ebola, Lassa, and Marburg viruses) was evaluated when administered on Days 1, 8, and 15 via intramuscular to rats. Intramuscular administration of 15 μ g/occasion EML-saRNA on three occasions over 2 weeks (7 days between each administration) resulted in mild transient loss of function in the dosed leg followed by swelling of the thigh for 2 to 3 days resulting in minimally to slightly increased incidence of localised inflammatory infiltrates at the dose sites and was well tolerated. Based on the absence of any adverse findings and under the conditions of this study, the no observed adverse effect level (NOAEL) is 5 μ g/dose for the LNP-MARVsaRNA-01 vaccine, the no observed adverse effect level (NOAEL) is 15 μ g/occasion for EML-saRNA. For further information please refer to the Investigators brochure (IB).

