4. STUDY OBJECTIVES

EML-Vac is a trial that is looking at new RNA vaccines against the Marburg, Ebola and Lassa viruses which are the major causes of viral haemorrhagic fever. The aim of the trial is to assess the safety of these vaccines alone and in combination, since this will be the first time that these have been used in humans. As this is a first-in-human trial, accrual will be limited to healthy adults between 18-50 years. Safety data will be assessed as an event rate and confidence interval with clear thresholds for pausing vaccinations in an individual and the trial (see Section 7.1.5). Provided the threshold for pausing vaccines in the trial is not crossed, immunogenicity will be determined by the quantity of binding antibodies 2 and 4 weeks after the last injection. As placebo does not inform the analysis for either of these endpoints, there will be no allocation to a placebo group. However, placebo doses of buffered saline will be administered I.M to ensure the participants remain blinded as to their group randomisation.

This trial is NOT looking at whether the vaccines are effective in terms of protection. It is just assessing whether and how well the immune system responds to the vaccine.

As exploratory endpoints, we will assess participants' neutralising antibody titres, B cell responses, and T cell responses to explore any associations with the induction of neutralising titres. We will also assess serum markers of innate response to both immunisations. Peripheral blood mononuclear cells (PBMCs) from participants will be processed for the isolation of antigen-specific B cells to isolate neutralising monoclonal antibodies to enhance understanding of targeted epitopes, with priority given to those showing higher serum neutralising antibody titres.

Objectives

- ➤ To evaluate the safety and immunogenicity of two immunisations with LNP-MARVsaRNA-01 administered IM 12 weeks apart at a 5 µg dose in 8 participants age 18-50 years.
- To evaluate the safety and immunogenicity of two immunisations with LNP-EBOVsaRNA-01 administered IM 12 weeks apart at one dose levels 4 μg in 8 participants age 18-50 years.
- To evaluate the safety and immunogenicity of two immunisations with LNP-LASSAsaRNA-01 administered IM 12 weeks apart at one dose levels 4 μg in 8 participants age 18-50 years.

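### Section 10.3.2 rules out hypothesis tests for immunogenicity and then names rank tests, a method that cannot show whether responses alone and in combination are similar

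*Protocol*

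**What the plan says.** Protocol section 10.3.2 (Immunogenicity) makes these statements in one paragraph:

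- Size: "A total of 40 participants will be included in the randomised evaluation of immunogenicity, 8 participants per group".
- Primary comparison: "The primary analysis will compare binding antibody responses to Ebola virus, Lassa virus and Marburg virus glycoproteins at 14 weeks", which the text equates with 2 weeks after the Week 12 booster.
- Main objective of Groups 1 to 5: whether responses to the individual "vaccines given alone are similar to those administered in combination".
- Testing: "No formal hypothesis testing will be performed for immunogenicity endpoints; all comparisons will be descriptive".
- Method for titres: "Titres of antigen specific antibodies will be described by timepoint and group and compared using rank tests, where appropriate".

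The only intervals the paragraph promises are for the proportion of responders within a group. It says that power for titre comparisons is hard to estimate and claims none.

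Two other places bear on the point. Section 4 says "immunogenicity will be determined by the quantity of binding antibodies 2 and 4 weeks after the last injection", whereas sections 2, 4.2, 10.2 and 10.3.2 give 2 weeks only. Section 3.1.6.1 reports that "in the pig model, cross-reactive Ebola-specific IgG was detected in animals immunised with LNP"-saRNA Marburg vaccine.

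**The concern.** There are two problems, and both lie in what the protocol states.

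First, the paragraph contradicts itself. It makes every immunogenicity comparison descriptive, without exception, and then has titres compared by a test. A statistical analysis plan that follows one sentence departs from the other.

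Second, the one between-group method named does not match the question asked. The question is similarity. A rank test looks for evidence of difference, and with 8 per group it will often find none when a real loss exists. It also gives no estimate of how large a loss remains possible, which is what a reader needs in order to judge whether the vaccines interfere with each other. What is at stake is how the main immunogenicity result can be reported. A non-significant p-value would leave the question open, yet it could easily be taken as an answer.

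**Working it through.** **Inputs from the protocol.** There are 8 participants per group. By Table 1, MARV is given to Groups 1, 4 and 5, EBOV to Groups 2, 4 and 5, and LASSA to Groups 3 and 5. The alone-versus-combination contrasts are therefore MARV G4/G1 and G5/G1, EBOV G4/G2 and G5/G2, and LASSA G5/G3. Each compares 8 with 8.

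**Assumed inputs.** The protocol gives no titre SD and no fold-loss of interest. I take log-normal titres, SD 0.3, 0.4 and 0.5 on the log10 scale, and a 2-fold loss as illustration.

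**Step 1: reproduce the protocol's own figure.** The Wilson interval at n = 8 (z = 1.96, z² = 3.84):

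- 8 of 8: lower limit = n/(n + z²) = 8/11.84 = 67.6%, upper limit 100%. Stated: 68–100%.
- 6 of 8: centre = (0.75 + 3.84/16)/(1 + 3.84/8) = 0.669; half-width = 1.96 × √(0.75 × 0.25/8 + 3.84/256)/1.48 = 0.260; interval 40.9–92.9%. Stated: 41–93%.

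Both agree. They describe responder proportions within one group and say nothing about a titre contrast between groups.

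**Step 2: what a rank test at 8 versus 8 can detect.** For the exact two-sided Mann-Whitney test the rejection region is U ≤ 13 or U ≥ 51, with exact size 0.0499. Power was simulated with 4,000 trials per cell (simulation error at most √(0.25/4000) = 0.8 percentage points).

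| SD (log10) | Power, 2-fold loss | Non-significant, 2-fold loss | Power, 4-fold loss |
|---|---|---|---|
| 0.3 | 44% | 56% | 94% |
| 0.4 | 28% | 72% | 78% |
| 0.5 | 19% | 81% | 58% |

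A separate run of 2,000 trials per cell gave 46%, 29% and 20% power at 2-fold.

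**Step 3: what an interval would show.** The 95% interval for the ratio of geometric means extends by a factor of 10^(t × SD × √(2/8)) either way, with t(0.975, 14 df) = 2.145:

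- SD 0.3: 10^(2.145 × 0.3 × 0.5) = 10^0.322 = 2.10
- SD 0.4: 10^0.429 = 2.69
- SD 0.5: 10^0.536 = 3.44

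Even with an observed ratio of exactly 1, the lower limit would be 1/2.10 = 0.48, 1/2.69 = 0.37 or 1/3.44 = 0.29. A halved response would not be excluded in any of the three cases. An interval shows this and a non-significant p-value hides it.

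**Step 4: would a formal equivalence test rescue the objective?** With a 2-fold margin and truly equal titres, two one-sided tests at n = 8 succeed in 24%, 4% and under 1% of trials at the three SDs. With a 3-fold margin the figures are 83%, 47% and 18%. Estimation with a stated precision is the realistic choice at this size.

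**The case against.** The strongest defence is that the words formal and where appropriate leave room for nominal p-values used as description. That reading is possible, but the protocol does not state it, and the sentence making all comparisons descriptive has no exception. One clause would settle it.

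A second defence is that the protocol claims no power, names no fold-loss of interest and says it is not sized for group differences. This stands: low power at 2-fold is not itself an error, and a 4-fold loss would be found more often than not at all three SDs. The point is the mismatch between objective and method.

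A third is that a t-based interval excludes a ratio of 1 about as often as the rank test rejects (46%, 29% and 20% against 45%, 28% and 19% at 2-fold in one set of simulations). That is correct. The gain is in what is reported and not in detection. Rank methods are also defensible where many titres sit at the assay floor, and the fix allows for that.

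Some stronger readings are tempting but not supported:

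- A reader might infer that the sponsor will call a non-significant result similar. No section says so.
- A reader might infer one test across all five groups, including groups that never received the antigen. No section prescribes it. The phrase about timepoint and group governs description, the objective itself names alone against combination, and section 10.4 leaves the full plan to the statistical analysis plan.
- A reader might infer from the pig finding that the EBOV contrast is biased. It is one observation without a magnitude, and whether cross-reactive antibody counts as part of the combination's response depends on the question asked. EBOV titres in Group 1 are not excluded from the description by group.
- A reader might think the primary timepoint is open. Section 10.3.2 fixes Week 14, so section 4 needs only alignment.

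**Conclusion.** The point holds on two grounds. Section 10.3.2 contradicts itself on hypothesis testing, which needs no assumption to see. The rank test it names also cannot answer the similarity question, and no between-group estimate or interval is promised alongside it. The size of the second problem rests on log-normal titres and assumed log10 SDs: over 0.3 to 0.5, a true 2-fold loss would pass as non-significant in about 56% to 81% of trials. That a non-significant difference is not evidence of similarity does not depend on those values. The undefined groups per contrast, the pig cross-reactivity and the timing in section 4 are matters for clarification and do not carry the finding. The change should be made, but nothing here puts the trial's design or data collection in doubt.

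**What to change.** In section 10.3.2:

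1. Delete the closing clause that compares titres by rank tests, or label those tests exploratory with nominal p-values. Keep the descriptive part of the sentence.
2. Name the Week 14 binding-IgG contrasts: MARV G4/G1 and G5/G1, EBOV G4/G2 and G5/G2, LASSA G5/G3. Report each as a geometric mean ratio with a 95% confidence interval, or as a rank-based shift estimate with its interval if many titres sit at the assay floor.
3. State the expected precision, about a factor of 2.1, 2.7 or 3.4 either way at log10 SD 0.3, 0.4 or 0.5, marked as an assumption.
4. Allow a conclusion of similarity only in terms of the fold-loss that the interval excludes. Do not add a formal equivalence test.

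As supporting changes, show Group 1 EBOV IgG beside the EBOV ratios because of the cross-reactivity reported in pigs. Align section 4 with the Week 14 primary timepoint, with Week 16 as supportive.

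The cost is protocol and analysis-plan wording plus a few lines of analysis. No participants or blood are added: the Table 2 visit totals leave 6 mL beyond safety and cellular samples at both visits (Week 14: 76 − 10 − 60 = 6; Week 16: 58 − 10 − 42 = 6), consistent with serum already being planned. The sponsor gives up only the freedom to state similarity without a bound.
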